3.4. Role of the patient's study partner

Every patient in the study must have a study partner, who must sign an ICF. As several of the outcome measures require input from the study partner, the study partner should be willing to actively participate in the study and must have sufficient patient interaction to be able to provide

meaningful input. The study partner should be willing to participate in every study visit that requires their input for efficacy measures as outlined in Table 2. The study partner is not required to attend all study procedures; examples include but are not limited to MRI, PET or lumbar procedures, skin or eye examinations. As outlined in inclusion criterion 21 (Section 4.1), the study partner must either co-habit with or have regular contact with the enrolled patient. As guidance, the study partner's ability to meet his/her expected responsibilities for this study would normally be possible when the study partner spends no less than 10 hours per week with the patient, divided over multiple days. While every effort should be made to maintain the same study partner for a given patient throughout the study, in the event of an unavoidable change in study partner, the new study partner should be thoroughly oriented to the purpose and requirements of the study and must sign an ICF. An identification code will be assigned to each study partner and recorded at each in-clinic study visit. Demographic data, including date of birth, sex, and relationship to the patient, will be collected for every study partner.

3.5. Discontinuation of the study

The study will be discontinued if the sponsor judges it necessary for medical, safety, regulatory, or other reasons consistent with applicable laws, regulations, and Good Clinical Practice (GCP).

The IDMC (see Section 12.4) will monitor the general safety of the patients in this study and provide ongoing review to confirm that the risks subjects face are not unreasonable in comparison to the potential benefits. The IDMC will do this by reviewing all safety events quarterly and at the formal interim analyses to determine evidence of any potential safety signals and their relative significance in terms of the overall benefit-risk profile of the drug. After each safety data review meeting, the IDMC will provide recommendations to the sponsor Executive Committee. The sponsor Executive Committee will be responsible for receiving and promptly acting on the IDMC recommendations. A potential outcome based upon the review of the IDMC recommendations includes stopping the study for safety reasons.

4. SUBJECT SELECTION CRITERIA

Study patients will be recruited by specialist clinics with extensive referral networks.

Investigators must keep a record of patients who were considered for enrollment (those that signed informed consent) but were never randomized. This information is necessary to establish that the patient population was selected without bias.

Each patient should meet all of the inclusion criteria and none of the exclusion criteria for this study. In general, there can be no exceptions to this rule. However, provision is made for rescreening of patients who did not meet entry criteria (see Section 3.2).

4.1. Inclusion criteria

For inclusion in the study, patients should fulfill the following criteria:

General

- [1] Provision of signed, written, and dated informed consent from patient and from study partner prior to any study specific procedures
- [2] Male or female, aged 55 to 85 years inclusive at signing of informed consent form (ICF)
- [3] For inclusion in optional genetic research, provision of specific signed, written, and dated informed consent

Diagnostic

- [4] Gradual and progressive change in the patient's memory function over more than 6 months, reported by patient and study partner
- [5] MMSE score of 20 to 30 inclusive at screening visit
- [6] Score of ≤85 on the Delayed Memory Index of the Repeatable Battery for the Assessment of Neuropsychological Status at screening visit
- [7] Inclusion criterion [7] has been deleted.
- [8] Inclusion criterion [8] has been deleted.
- [9] For a diagnosis of mild AD, patient (1) meets the National Institute on Aging (NIA) and the Alzheimer's Association (AA) (NIA-AA) criteria for probable AD and (2) has a CDR global score of 0.5 or 1, with the memory box score ≥0.5 at the screening visit
- [10] For a diagnosis of MCI due to AD, patient (1) meets NIA-AA criteria for MCI due to AD and (2) has a CDR global score of 0.5, with the memory box score ≥0.5 at the screening visit
- [11] Inclusion criterion [11] has been deleted.

- [12] Laboratory tests show no evidence of other etiologies for MCI or dementia, including but not limited to vitamin B12 level. Patients may be enrolled if the investigator considers that the abnormal values are not the cause of cognitive symptoms.
- [13] PET visual reading or CSF $A\beta_{1-42}$ concentration positive for presence of amyloid. Please see the laboratory manual for further details.

Note: For inclusion, amyloid positivity criteria must be met by either amyloid PET imaging or by CSF $A\beta_{1-42}$ concentration (both are not required). If a patient does not meet amyloid positivity criteria according to the first test applied (either amyloid PET or CSF $A\beta_{1-42}$ concentration), the other amyloid test cannot be performed.

Contraception and concomitant medication

- [14] Women must be postmenopausal or surgically sterile or infertile due to congenital anomaly. A postmenopausal woman is defined as having an intact uterus, who has not taken hormones or oral contraceptives within 1 year, and who has had either cessation of menses for at least 1 year, or 6 months of spontaneous amenorrhea with follicle-stimulating hormone (FSH) value that indicates the woman is postmenopausal. Surgically sterile women are defined as those who have had a hysterectomy, bilateral ovariectomy (oophorectomy), or bilateral tubal ligation.
- [15] Men must abstain or be willing to use barrier contraception (ie, condoms), from the first day of dosing until 3 months after the last dose of study treatment. They must also be willing to abstain for 24 hours after PET scans. For this protocol, sexual abstinence is defined as refraining from heterosexual intercourse during the entire period of risk associated with the study treatment. True abstinence is only acceptable when it is in line with the patient's usual and preferred lifestyle. Given the length of the study, the reliability of patients to adhere to this provision should be considered by the investigator.
- [16] All medication dosing should be stable for at least 30 days before screening, and between screening and randomization (does not apply to medications discontinued during screening, medications taken as needed, and/or medications not expected to substantially influence safety or efficacy assessments, in the opinion of the investigator, at baseline).
- [17] Treatment with memantine must be discontinued at least 3 weeks before randomization.

Procedural

- [18] Patient agrees to undergo APOE genotyping
- [19] For patients undergoing florbetapir F 18 amyloid PET for entry or as part of the PET sub-study: able and willing to travel to a PET imaging center and complete the planned scanning sessions, and with past and planned exposure to ionizing radiation not exceeding safe and permissible levels

- [20] Must have completed 6 years of formal education and/or have a history of academic achievement and/or employment sufficient to exclude intellectual disability
- [21] The patient must have a reliable study partner with whom he/she cohabits or has regular contact (combination of face-to-face visits/ telephone contact acceptable). If at all possible, the same study partner should be willing to participate throughout the study and must have sufficient patient interaction to be able to provide meaningful input into the rating scales administered in this study, where study partner input is required, in particular for the CDR. As guidance, the ability for a study partner to meet his/her expected responsibilities for this study would normally be possible when the study partner spends no less than 10 hours per week with the subject, divided over multiple days. Evidence for adequacy of the study partner should be documented in source documentation.
- [22] Patient and study partner must be able to read, write, and speak the language in which psychometric tests are provided, with acceptable visual and auditory acuity (corrected).
- [23] Study partner must be cognitively able to fulfill the requirements of the study.
- [24] In the opinion of the investigator, the patient and study partner will be compliant with, and have a high probability of completing, the study

4.2. Exclusion criteria

Patients should not enter the study if any of the following exclusion criteria are fulfilled:

General

- [1] Patients should not have participated or currently participate in any other clinical trial or any other type of medical research judged not to be scientifically or medically compatible with this study at screening or for the duration of their participation in the current study.
- [2] Investigator site personnel directly affiliated with this study and/or their immediate families. Immediate family is defined as a spouse, parent, child, or sibling, whether biological or legally adopted. Employees or study partner of AstraZeneca, Lilly, or any third-party organizations involved in the study.

Medical

- [3] Significant and/or current neurological disease affecting the CNS, other than AD, that may affect cognition or ability to complete the study, including but not limited to, other dementias, serious infection of the brain, Parkinson's disease, or epilepsy or recurrent seizures (except febrile childhood seizures)
- [4] History of clinically evident stroke, or multiple strokes based on history or imaging results.

- [5] History of clinically important carotid or vertebrobasilar stenosis or plaque. Patients with evidence of a carotid bruit at screening should undergo an ultrasound prior to randomization.
- [6] History of multiple concussions or a concussion with sustained cognitive complaints or objective change in neuropsychological function in the last 5 years
- [7] Patients with a current Diagnostic and Statistical Manual of Mental Disorders, Fifth Edition (DSM-V) diagnosis of Major Depressive Disorder (MDD) or any current primary psychiatric diagnosis other than AD (as per DSM-V) if, in the judgment of the investigator, the psychiatric disorder or symptom is likely to confound interpretation of drug effect, affect cognitive assessment, or affect the patient's ability to complete the study. Patients with history of schizophrenia or other chronic psychosis are excluded.
- [8] History of alcohol, drug abuse or dependence (except nicotine dependence) (as per DSM-V) within 2 years before the screening visit
- [9] Within 1 year before the screening visit or between screening and baseline, any of the following: myocardial infarction; moderate or severe congestive heart failure, NYHA class III or IV; hospitalization for, or symptoms of, unstable angina; syncope due to orthostatic hypotension or unexplained syncope; known significant structural heart disease (eg, significant valvular disease, hypertrophic cardiomyopathy); or hospitalization for arrhythmia
- [10] Congenital QT prolongation
- [11] Intermittent second- or third-degree atrioventricular (AV) heart block or AV dissociation or history of ventricular tachycardia
- [12] Exclusion criterion [12] has been deleted.
- [13] History of cancer within the last 5 years, with the exception of non-metastatic basal and/or squamous cell carcinoma of the skin, in situ cervical cancer, non-progressive prostate cancer or other cancers with low-risk of recurrence or spread.
- Current serious or unstable clinically important systemic illness that, in the judgment of the investigator, is likely to affect cognitive assessment, deteriorate, or affect the patient's safety or ability to complete the study, including hepatic, renal, gastroenterologic, respiratory, cardiovascular, endocrinologic, immunologic, or hematologic disorders
- [15] History of vitiligo and/or current evidence of post-inflammatory hypopigmentation or exposure to depigmenting agents, eg, hydroquinone, in the 6 months prior to screening
- [16] History of 2 or more clinically important drug allergies, eg, severe drug-induced rash or anaphylaxis

MRI, vital signs, electrocardiogram, and laboratory tests, physical examination

- [17] Screening MRI shows evidence of significant abnormality that would suggest another potential etiology for MCI or dementia, such as >5 microhemorrhages; prior macrohemorrhage (>1 cm³); ≥4 lacunar infarcts, or single infarct >1 cm³; evidence of cerebral contusion, encephalomalacia, aneurysms, vascular malformation, or clinically significant space-occupying lesions
- [18] Uncontrolled hypertension, ie, supine systolic blood pressure >165 mmHg or diastolic blood pressure >95 mmHg. If an initial blood pressure reading is higher than this, the lowest value from 3 additional attempts to get a rested (>5 min), supine blood pressure reading should be used before excluding a patient for uncontrolled hypertension.
- [19] A corrected QT (QTcF) interval measurement >470 msec (men and women) at screening (as determined at the investigational site). The site may request a central read prior making determination of this exclusion.
- [20] Known positive serologic findings for human immunodeficiency virus (HIV) antibodies
- [21] Positive hepatitis B surface antigen (HBsAg) or hepatitis C virus (HCV) antibodies. Note: Patients with positive HCV antibodies may have a follow-up polymerase chain reaction (PCR) test ordered. If the PCR is negative, they are not excluded.
- [22] Urine drug screen positive for inappropriate drug use.
- [23] Any clinically important abnormality at screening, as determined by investigator, in physical or neurological examination, vital sign, ECG, or clinical laboratory test results that could be detrimental to the patient or could compromise the study
- [24] Calculated creatinine clearance <30 mL/min (Cockcroft-Gault formula; Cockcroft and Gault 1976)
- [25] ALT \geq 2 × the upper limit of normal (ULN) of the performing laboratory, AST \geq 2 × ULN, total bilirubin \geq 1.5 × ULN, or ALP \geq 1.5x ULN at screening

Concomitant medications

- [26] Clinician impression of use of medications (eg, sleep aids, narcotics, anxiolytics etc.) in a manner that would interfere with cognitive testing.
- [27] Use of strong inhibitors of CYP3A4 within 14 days or 5 half-lives, whichever is longer, before randomization, or of strong inducers of CYP3A4 within 30 days before randomization.
- [28] Use of strong inhibitors of Pgp or BCRP within 14 days or 5 half-lives, whichever is longer, prior to randomization, or inducers of Pgp within 30 days before baseline.
- [29] Exclusion criterion [29] has been deleted.

- [30] For patients who will undergo lumbar puncture for CSF collection, use of medications known to significantly influence coagulation, such as warfarin or heparin.

 Anti-platelet inhibitors, such as aspirin, dipyridamole, or clopidogrel, are allowed, but they may require washout prior to lumbar puncture, at the investigator's discretion.
- [31] Treatment with any investigational drug or device within 60 days or 5 half-lives prior to screening (whichever is longer) or between screening and randomization.
- [32] Prior treatment with an AD vaccine. Prior treatment with a passive anti-amyloid immunotherapy is allowed if completed at least 5 half-lives prior to randomization.

Procedural

[33] Presence of any of the following MRI contraindications: pacemaker; cardiac defibrillator; spinal cord or vagus nerve stimulator; aneurysm clip; artificial heart valve; coronary or carotid stents that are not compatible with MRI; ear implant; CSF shunt; other implanted medical device (eg, Swan Ganz catheter, insulin pump); metal fragments or foreign objects in the eyes, skin, or body; severe claustrophobia that would contraindicate a brain MRI scan; or other contraindications due to local requirements

Additional exclusion criteria for patients undergoing CSF sampling at inclusion or participating in the CSF sub-study are as follows:

- [34] Any spinal malformations or other aspects (eg, tattoos) or other clinical findings (eg, papilledema seen with ophthalmoscopy) that may complicate or contraindicate lumbar puncture, as judged by the investigator
- [35] Current blood-clotting or bleeding disorder, including clinically significant abnormal findings in laboratory assessments of coagulation or hematology

Additional exclusion criteria for patients using amyloid PET for inclusion or participating in the florbetapir F 18 amyloid PET sub-study are as follows:

- [36] Present or planned participation in a research and/or medical protocol involving PET ligands or radioactive agents, judged not to be scientifically or medically compatible with this study
- [37] Have planned or are planning to have exposure to ionizing radiation that, in combination with the planned administration of study amyloid PET ligand, would result in a cumulative exposure that exceeds local recommended exposure limits
- [38] For patients who will obtain a florbetapir F 18 scan: hypersensitivity to the active substance or any of the excipients of florbetapir F 18.

For procedures for withdrawal of incorrectly enrolled patients, see Section 5.3.

5. STUDY CONDUCT

5.1. Restrictions during the study

Patients will be required to:

- Refrain from donating blood from the screening visit until 3 months after the followup visit
- Follow restrictions regarding concomitant medications according to Section 5.6
- Avoid use of tanning beds and self-tanning products
- 4. Wear a hat and appropriate clothing when exposed to sunlight; use a sunscreen with a sun protection factor (SPF) of at least 15; and protect the lips with a lip balm containing sun block
- Men must abstain or be willing to use barrier contraception (ie, condoms) and not donate sperm during the study participation, through 3 months after study participation ends. Men must also agree to abstain for 24 hours after PET scans.
- 6. Avoid excessive use of alcohol during study participation. Excessive alcohol consumption is defined for men as consuming an average of more than 3 drinks per day, or more than 21 drinks per week. For women, excessive use of alcohol is defined as consuming an average of more than 2 drinks per day, or more than 14 drinks per week.

5.2. Patient enrollment and randomization

5.2.1. Procedures for enrollment

Additional information for the procedures for enrollment can be found in Section 3.2.1 and the Study Plan (Table 2)

5.2.2. Procedures for randomization

Patient eligibility will be established before randomized treatment assignment (see Section 4 for inclusion and exclusion criteria). The randomization will be stratified for disease status at baseline (MCI due to AD or mild AD).

The stratified randomization schedule will be prepared by the CCl Biostatistics

Department on behalf of the sponsor. Randomization codes will be allocated in blocks within strata to AZD3293 20 mg, AZD3293 50 mg, or placebo in a ratio of 1:1:1, stratified by MCI due to AD and mild AD dementia. Enrollment rates in MCI due to AD and mild AD strata will be monitored.

If a patient withdraws from the study, the patient's study identifier and randomization code will not be reused, and the patient will not be allowed to re-enter the study.

5.3. Procedures for handling subjects incorrectly enrolled or entered

Patients who fail to meet the inclusion/exclusion criteria should not, under any circumstances, be enrolled or receive study medication. There can be no exceptions to this rule.

Patients who are incorrectly entered but are not yet randomized or initiated on treatment should not participate in any further study-related procedures and should be withdrawn from the study.

Where patients who do not meet the study inclusion and/or exclusion criteria are enrolled in error or incorrectly started on treatment, or where patients subsequently fail to meet the study criteria post initiation, the investigator should inform the CC medical monitor immediately. The medical monitor is to ensure all such contacts are appropriately documented. The medical monitor, the sponsor's clinical research physician/scientist, and the investigator will determine whether the patient may continue in the study, with or without investigational product. Inadvertently enrolled patients may be maintained in the study and on investigational product when the CC medical monitor and sponsor's clinical research physician/scientist agree with the investigator that it is medically appropriate for that patient. The patient may not continue in the study with or without investigational product if the medical monitor and sponsor's clinical research physician/scientist do not agree with the investigator's determination it is medically appropriate for the subject to continue. The investigator must obtain documented approval from the sponsor's clinical research physician/scientist to allow the inadvertently enrolled patient to continue in the study with or without investigational product.

Safety information may be collected for 30 days after treatment discontinuation to ensure adequate follow-up.

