5.8. Discontinuation of study treatment

Patients must be discontinued from study treatment in the following situations:

- Patient decision. The patient is at any time free to discontinue treatment, without prejudice to further routine clinical care.
- Adverse event or clinically significant laboratory value, ECG result, or vital sign
 measurement of such severity that, in the opinion of the investigator or medical monitor,
 continued treatment is not in the best interest of the patient
- Severe non-compliance to the study protocol that results in a safety concern, in the judgment of the investigator
- The patient, for any reason, requires a treatment with an excluded therapeutic agent for which temporary suspension of study treatment cannot be achieved (see Section 5.9). In this case, discontinuation from study drug occurs prior to introduction of the new agent.
- The patient develops a significant uncontrolled medical condition, such as a
 neuropsychiatric disorder that meets one of the exclusion criteria that in the opinion of
 the investigator after appropriate medical assessment, would pose an unacceptable risk to
 the patient if they were to continue receiving study drug.

Patients may be discontinued from study treatment in the following situations:

- An individual patient enrolled in the study may be discontinued from dosing based on a specific AE profile, as recommended by the IDMC, the CC medical monitor, and/or the sponsor Global Study Physician/Scientist, in discussions with the Principal Investigator.
- Incorrect enrollment (Section 5.3)
- Vasogenic edema (Section 6.4.3.7)
- Elevated liver enzymes (Section 6.4.5.1)

The study may be paused or stopped by either the IDMC or the sponsor at any time.

Procedures for discontinuation

A patient who decides to discontinue study treatment will always be asked about the reason(s) and the presence of any AEs. Any reported AEs will be followed up (See Sections 6.4.3 and 6.4.4).

All study medication should be returned to the investigational site.

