Patients should be encouraged to remain in the study until Week 104 (Visit 20), even if study treatment has been discontinued, and they should continue to participate in scheduled visits as described in Table 2. Patients who agree to remain in the study after discontinuing study treatment should continue to participate in scheduled visits and assessments, as appropriate, with the exception of PK measurements and PET scans, after completing the early discontinuation assessments described in Table 2, as appropriate. The Collection medical monitor may be consulted regarding the details of managing a specific patient who discontinues treatment but remains in the study.

Only patients on study treatment through Week 104 (Visit 20) are eligible to participate in the extension Study AZFD. For those who continue into Study AZFD, the follow-up visit in Study AZES is not required. However, Study AZES study must be completed prior to entering Study AZFD.

Patients in Study AZES who complete Week 104 procedures (Visit 20) will be considered study completers; any statements regarding early discontinuation requirements do not apply to these patients.

Patients who choose to withdraw from the study upon discontinuing study treatment and after completing the early discontinuation Visit assessments, as appropriate, should be asked to return for a follow-up visit (Visit 21) within 4 to 6 weeks of discontinuing treatment. If a patient withdraws his or her consent to participate in the study, see Section 5.10.

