12.2.4. Efficacy

All analyses will be performed in a manner that is consistent with the intent-to-treat (ITT) principle. An ITT analysis is an analysis of data by the groups to which patients are assigned by random allocation, even if a patient does not take the assigned treatment or does not receive the correct treatment, or otherwise does not follow the protocol or is not followed to the end of the study (ie, Week 104). If a treatment group is dropped at an interim analysis, the data from those patients will be analyzed according to the treatment group to which the patients were originally randomized. When change from baseline is assessed, a modified ITT (mITT) approach will be used; patients will be included in the analysis only if both a baseline and a post-baseline measure are available.

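### Where the physicians do not agree that an incorrectly enrolled patient should continue, Section 5.3 ends follow-up as well as drug, at odds with Section 5.8, and can lose Week 104 data

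*Protocol*

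**What the plan says.** Protocol Section 5.3 covers patients enrolled or started on treatment in error, "or where patients subsequently fail to meet the study criteria post initiation". The medical monitor must be told at once. The monitor, the sponsor's physician or scientist and the investigator "will determine whether the patient may continue in the study, with or without investigational product". If they agree that it is medically appropriate, "Inadvertently enrolled patients may be maintained in the study and on investigational product". The removal rule reads "The patient may not continue in the study with or without investigational product"; it applies only when the monitor and the sponsor's physician or scientist dispute the investigator's view that continuing is appropriate. The investigator also needs documented sponsor approval for such a patient to stay in the study even off drug. The section names no follow-up beyond optional safety data over 30 days after drug is stopped.

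Protocol Section 5.8 has a list of reasons why study treatment may be stopped. One entry is "Incorrect enrollment (Section 5.3". The same section then says: "Patients should be encouraged to remain in the study until Week 104 (Visit 20), even if study treatment has been discontinued". Table 2 footnote d repeats this, with PK measurements and PET scans excepted. Section 9.2 has investigators instructed to retain patients off treatment and keep missing data low.

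Two other places use Section 5.3 as a procedure for leaving the study: the closing line of Section 4.2 (exclusion criteria) and Section 13.3.1 (maternal exposure).

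**The concern.** Section 5.3 uses one judgement, whether continuing is medically appropriate, to settle two questions: whether the patient takes the drug, and whether the patient is followed. In the no-agreement branch both end together. Section 5.8 keeps them apart and asks for follow-up to Week 104 once drug has stopped.

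What is at stake is the completeness of the primary endpoint, change in ADAS-Cog13 at Week 104. A patient removed under Section 5.3 loses that measurement through a decision made by others after randomisation. The MMRM must then treat the missing scores as missing at random, and the sensitivity analysis in Section 12.2.4.1 must impute them from placebo data, when scores off drug could have been collected.

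**Working it through.** **Passages side by side**

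| Place in protocol | What stops | Follow-up after that |
|---|---|---|
| 5.3, parties agree | Nothing, or drug only | Patient stays in the study |
| 5.3, no agreement | Drug and study | Optional safety data, 30 days |
| 5.8, incorrect enrolment | Drug | Encouraged to stay to Week 104 |
| Table 2 footnote d | Drug | Scheduled visits as appropriate, without PK and PET |
| 4.2 closing line; 13.3.1 | Study, citing 5.3 | Not given for incorrect enrolment; pregnancy outcome is followed in 13.3.1 |

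The second row does not fit the third and fourth.

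**When the loss is total.** Table 2 places the first post-baseline ADAS-Cog13 at Visit 6 (Week 13). Footnote d gives it at the early discontinuation visit only if more than 12 weeks have passed since the last administration. A patient removed within about 12 weeks of the Visit 2 baseline therefore normally has no post-baseline score. Sections 12.1.1 and 12.2.4 require one, so that patient leaves the modified ITT analysis. A patient removed later stays in the model but without Week 104.

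**Reproducing the plan's power.** Inputs from Section 12.3.1: 734 per group, α = 0.025 per dose, adjusted effect size 0.21, stated power 96%. Sidedness is not given there; two-sided is assumed.

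- Power = Φ(ES × √(n/2) − z), with z = 2.241 for two-sided 0.025.
- 0.21 × √367 = 4.023, and Φ(4.023 − 2.241) = 96.3%. The stated figure reproduces.
- The effect size also reproduces: (0.65 × 3.83/13.54 + 0.35 × 2.24/12.96) × (1 − 0.5 × 0.30) = 0.208. This borrows the 30% dropout rate that Section 12.3.2.3 states for MRI.

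**Scale of a possible loss.** The documents give no rate for Section 5.3 removals. For an assumed share x of 1% to 5%, the trial total is 2202 × 0.01 = 22 to 2202 × 0.05 = 110 patients.

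- (a) These patients give no usable data: n = 734 × (1 − x), effect size 0.21.
- (b) They are extra dropouts with half the effect: dropout = 0.30 + 0.70x, effect size = 0.2444 × (1 − 0.5 × dropout), n = 734.

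| x | Patients per arm | Power (a) | Power (b) |
|---|---|---|---|
| 0 | 0 | 96.3% | 95.9% |
| 1% | 7 | 96.1% | 95.7% |
| 2% | 15 | 95.9% | 95.6% |
| 5% | 37 | 95.3% | 95.1% |

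The fall is 0.2 to 0.9 points under (a) and about 0.1 to 0.8 under (b).

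**The case against.** The strongest reply is that the clause is narrow. Removal needs the investigator to favour continuing and the monitor and sponsor physician not to agree. Otherwise Section 5.3 already allows the patient to stay, on or off drug. The Section 5.8 entry points back to Section 5.3, so a specific rule may be said to override a general one. No site decides alone, so differing practice between sites is not shown. All of this stands, and it limits the size of the point. It does not explain why a disagreement about drug should also end assessments off drug.

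Three stronger readings are tempting, and the documents do not support them.

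- **That Section 5.3 removes patients as a general rule, including anyone who later fails an entry criterion.** Later failure triggers notification and a decision. Section 6.4.7 says new ECG findings outside the entry criteria do not by themselves mean discontinuation. The removal sentence also sits between two sentences about inadvertently enrolled patients.
- **That the ITT rule is broken.** Section 12.2.4 analyses patients by assigned group "even if a patient does not take the assigned treatment or does not receive the correct treatment, or otherwise does not follow the protocol", and the same sentence goes on to cover patients not followed to Week 104. Section 5.3 excludes no one from analysis.
- **That removal depends on treatment arm.** The QTcF and liver exclusions (19 and 25) are fixed at screening, and later ECG and liver changes have their own pathways (Sections 6.4.7 and 6.4.5.1). An enrolment error exists before randomisation, and sites and sponsor are blinded. Even if removal were assumed to be 3% on an active arm and 1% on placebo, with removed patients 5 points away from the model's prediction, the shift would be (0.03 − 0.01) × 5 = 0.1 point, against assumed effects of 2.24 to 3.83 points.

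It is also fair to say that visits off drug are not free of medical concern. MRI and, in the CSF sub-study, lumbar puncture stay on the schedule, and a patient enrolled despite a contraindication should not have them. The fix must allow for that.

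**Conclusion.** The point holds in a limited form. Where agreement is not reached, Section 5.3 ends follow-up as well as drug for a randomised patient. This is at odds with Section 5.8, Table 2 footnote d and Section 9.2, and Sections 4.2 and 13.3.1 add to the confusion by citing Section 5.3 as a way out of the study. The harm is avoidable, discretionary missing ADAS-Cog13 data after randomisation, and a patient removed before any post-baseline score leaves the modified ITT analysis.

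The size is unknown and probably small: under about 1 point of power if 1% to 5% of patients were affected. That range is an assumption. No figure in the protocol is wrong on this point. Severity is low; the change is worth making because it is cheap.

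**What to change.** Reconcile Section 5.3 with Section 5.8 so that two decisions are stated separately.

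- **Investigational product:** leave this with the physicians, as now written.
- **Follow-up:** add that, unless consent is withdrawn, a randomised patient is asked to complete the early discontinuation visit and the scheduled assessments to Week 104, as appropriate under Section 5.8, omitting any procedure medically unsuitable for that patient.

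Then align the cross-references in Sections 4.2, 5.8 and 13.3.1, so that each says whether it means leaving treatment or leaving the study. Which of the two applies in Section 13.3.1 is for the sponsor to settle.

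The cost is a sentence or two in the next amendment, plus visits that are already scheduled for a few patients off drug.
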